9.3 POPULATIONS FOR ANALYSES

For purposes of analysis, the following populations are defined in [Table 13](#).

Table 13 Analysis Populations

Analysis Population	Description
Efficacy	All participants who received at least one dose of RO7296682 in combination with atezolizumab, and who have at least one baseline and one on-study tumor assessment. Participants who received at least one dose of RO7296682/atezolizumab and discontinued the study because of progression before the first on-study tumor assessment will be considered response-evaluable.
DLT evaluable	DLT evaluable participants are those who have completed the DLT period with two administrations of RO7296682/atezolizumab without DLT, or participants reported with a DLT. This population will be used in the determination of the MTD and/or RP2D.
Safety	All participants who received at least one dose of study treatment, whether prematurely withdrawn from the study or not, will be included in the safety analysis.
Pharmacokinetic	All participants who have received at least one dose of study treatment and who have data from at least one post-dose sample will be included in the PK analysis population. Participants will be excluded from the PK analysis population if they significantly violate the inclusion or exclusion criteria, deviate significantly from the protocol, or if data are unavailable or incomplete which may influence the PK analysis. Excluded cases will be documented together with the reason for exclusion. All decisions on exclusions from the analysis will be made prior to database closure.
Immunogenicity	The immunogenicity analyses will include all participants with at least one ADA assessment, irrespective of whether or not the participant receives any treatment. Excluded cases will be documented together with the reason for exclusion.
Pharmacodynamic	All participants who had at least one pre-dose and one post-dose PD assessment will be included and analyzed according to the treatment they actually received.

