- Fresh tumor biopsy: Mandatory fresh tumor biopsy samples must be obtained for all participants enrolled in Part II and Part III at baseline and on treatment from a safely accessible site and after participant's consent (see Section 1.3). In Part II specifically, the samples collected at baseline will reflect the most recent immune phenotype ([REDACTED]) of the participant. Should the immune phenotype of the fresh biopsy be other than [REDACTED] (as evaluated by the archival sample), the particular participant will be assessed in a separate efficacy analysis population. Furthermore, in Part II and Part III the samples will be assessed for treatment-induced changes in immune cell numbers, lineage and activation characteristics, as well as changes in tumor markers such as PD-L1 and expression of Fc γ R, TCR V β repertoire. (The analyses will be performed with respect to changes in the characteristics of lineage [REDACTED], activation [REDACTED] differentiation [REDACTED] expression of Fc γ R, TCR V β repertoire).
- Healthy skin punch biopsy: Mandatory fresh skin biopsy samples must be obtained at baseline and on treatment for all participants enrolled in all Parts of the study after participant's consent (see Section 1.3). These samples will be assessed for treatment-induced changes in immune cell numbers, composition, and functional immune cell characteristics. The analyses will be undertaken by immunohistochemistry and/or genetic and genomic methods (see Section 8.7).

Residual plasma/serum samples (e.g. from PK and/or PD assessments) may be used for retrospective and longitudinal testing of bacterial or viral infection (including SARS-CoV-2) by serological methods. This testing may be performed for each participant. In addition to serving as an important safety measure, these analyses will inform as to any association of bacterial or viral infection and response to RO7296682 in combination with atezolizumab. In addition, residual blood, serum/plasma, tissue, and stool samples may also be used for additional (assay) validation experiments after the specified

analyses were performed. Details on sampling procedures, sample storage, and shipment are given in the Study Flow Chart and Laboratory Manual.

These samples will be destroyed within 2 years after the date of final CSR unless the participant gives specific consent for the remainder of the sample(s) to be stored for optional exploratory research within the RBR (see Section 8.9).

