9.2 SAMPLE SIZE DETERMINATION

Part I:

The maximum total number of participants in the dose escalation portions of Part I will be approximately 60 DLT-evaluable participants on a Q3W schedule. The exact sample size cannot be pre-determined and depends on the number of cohorts needed to reach

a MTD and/or RP2D. However, the simulations presented in Section 3 of [Appendix 11](#) show simulated sample sizes in a variety of toxicity scenarios.

Part II:

Approximately 60 CPI-experienced participants with NSCLC, HNSCC, and MEL will be enrolled in Part II in order to have around 10 participants per indication and aim for at least 30 response-evaluable participants with an ██████████, which is confirmed in the fresh baseline biopsy. With around 10 participants per indication, there will be sufficient number for decision making to open Part III cohorts ([Table 18](#)). Participants with MEL, NSCLC and HNSCC which are not amenable to standard treatment, will be enrolled in Part II; however, if emerging data suggest alternative indications should be pursued, then participants with ovarian, esophageal, TNBC or other indications as deemed fit may be considered.

Part III

In Part III, each tumor-specific cohort for NSCLC, HNSCC, and MEL may be opened for approximately 20 response-evaluable participants given that any of the gating criteria defined in [Section 9.5](#) are met based on the corresponding indication in single agent dose expansion of WP41188, Part I of this study, or Part II of this study. The futility interim analysis will be performed when the first 10 response-evaluable participants have mature data in each tumor-specific cohort. The detail of the futility analysis is provided in [Section 9.5](#).

For the CPI-experienced HNSCC cohort in Part III, the sample size of 20 response-evaluable participants allows to declare futility with a probability of 92% under the assumption that the true ORR is 5%, based on the posterior probability for ORR to be below 20% with a 70% confidence level.

For CPI-experienced NSCLC cohort in Part III, the sample size of 20 response-evaluable participants allows to declare futility with a probability of 87% chances under the assumption that the true ORR is 10%, based on the posterior probability for ORR to be below 25% with a 70% confidence level.

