9.4.2 Efficacy Analyses

The primary and secondary efficacy analyses listed in [Table 14](#) will include all participants in the efficacy population with participants grouped according to dose cohort (and schedule if applicable) within each study part.

Table 14 Efficacy Statistical Analysis Methods

Endpoint	Statistical Analysis Methods
According to RECIST Version 1.1 criteria (Appendix 13) and iRECIST (Appendix 14) 
• Objective response rate (ORR)• Disease control rate (DCR)• Duration of response (DoR)• On treatment progression free survival (PFS)	No formal statistical model and no formal hypothesis testing are planned in this study. Tumor response data will be reported using descriptive statistics. Response data will be listed. Participants with missing or no response assessments will be classified as not evaluable unless there is documented clinical deterioration, in which case participant will be classified as non-responders. Reasons for the non-evaluability will be summarized (e.g., withdrawal of consent, study discontinuation because of AE or physician decision). ORR and DCR will be summarized by using relative frequencies and 90% confidence interval (CI). Duration of response and PFS (on-treatment) will be summarized by using time-to-event analyses and Kaplan-Meier curves.
• Overall Survival (OS) (if available)	OS data may be tabulated and summarized using time-to-event analyses and Kaplan-Meier curves if data are collected and mature. Summaries will be carried out by cohort (and schedule if applicable) separately for each part.

Objective response rate (ORR) is determined as the rate of participants with an overall response of CR or PR. DCR is determined as the rate of participants with an overall response of either CR, PR, or SD rate. ORR and DCR will be derived for RECIST v1.1 and will be based on Investigators' assessment. Objective response (OR) is defined as a CR or PR as determined by the Investigator. For this protocol, confirmation of response is required at least 4 weeks after a first response occurred. To classify a response as SD, measurements will have to be classified as stable (according to RECIST v1.1) at least once after study entry at a minimum of 6 weeks after study entry. Participants with missing or no response assessments will be classified as not evaluable unless there is documented clinical deterioration, in which case participants will be classified as non-responders.

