DoR will be calculated for participants who have a best overall response of CR or PR and defined as the time from first occurrence of a documented OR until the time of

documented disease progression or death (death within 30 days from last study treatment) from any cause, whichever occurs first. Censoring methods will be the same as the one applied for progression-free survival (PFS; on-treatment).

PFS on treatment will be defined as the time from study treatment initiation (C1D1) to the first occurrence of documented disease progression (based on RECIST v1.1 Investigator's assessment) or death from any cause, whichever occurs first. For participants who do not have documented progressive disease or death (within 30 days from last study treatment) during the study, PFS will be censored at the day of the last tumor assessment. Participants without any post baseline assessments or with all post-baseline assessments having unknown result/response but known to be alive at the clinical cut off for the analysis will be censored at the date of study treatment initiation plus one day.

Sensitivity analyses of response endpoints (ORR, DCR, DoR, and PFS) may include the evaluation of response according to iRECIST and the evaluation of response from an independent centralized review.

OS is defined as the time from the first dose of study treatment to the time of death from any cause. Participants who are still alive at the time of analysis will be censored at the time of their last study assessment (for active participants) or at the last date known alive (for participants in follow-up).

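### The efficacy population leaves out treated participants with no on-study scan unless they left for progression, so the primary ORR can match or exceed the all-treated rate but never fall below it, and no all-treated ORR is planned

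*Combined protocol and SAP*

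**What the plan says.** Table 13 defines the efficacy population as participants who received at least one dose of the combination "and who have at least one baseline and one on-study tumor assessment". It adds one group without an on-study scan: those who discontinued the study because of progression before the scan was due.

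Section 9.4.2 states that the primary and secondary efficacy analyses "will include all participants in the efficacy population with participants grouped according to dose cohort". ORR is primary in Parts II and III (Section 3, Table 4). DCR, DoR, PFS and OS are analysed on the same set.

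Section 9.4.2 then gives rules for participants without a response assessment:

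- "Participants with missing or no response assessments will be classified as not evaluable unless there is documented clinical deterioration"; with documented deterioration they are non-responders.
- In Table 14, "Reasons for the non-evaluability will be summarized". The examples given are withdrawal of consent and leaving the study for an adverse event or on a physician's decision.
- For PFS, a censoring rule covers "Participants without any post baseline assessments or with all post-baseline assessments having unknown result/response but known to be alive" at the data cut-off.

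On sensitivity analyses it says only: "Sensitivity analyses of response endpoints (ORR, DCR, DoR, and PFS) may include the evaluation of response according to iRECIST", plus independent central review. Neither changes the population.

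**The concern.** Tumor assessments are due every 8 weeks (Section 8.1.1). Before the first one, a treated participant may die without recorded progression, withdraw consent (after which Section 7.2 stops all follow-up) or be lost. As Table 13 is written, each of these leaves the ORR and DCR denominators, and none of them can have responded.

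The two sections also do not fit together. A participant with no scan and documented clinical deterioration, who did not discontinue because of progression, is a non-responder under Section 9.4.2 but is absent from Table 13's population. The text never says whether not-evaluable participants count in the denominator, so two statisticians could report two primary ORRs from the same data.

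At stake is the main efficacy estimate and its 90% CI, not a hypothesis test. For PFS and OS, early deaths without recorded progression drop out, although OS needs no scan at all.

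**Working it through.** **1. The plan's own figures on the response-evaluable base.** Section 9.2 states futility probabilities of 92%, 87% and 83% with 20 response-evaluable participants. Section 9.5 sets final futility at fewer than 3, 4 and 5 responders. Exact binomial with n = 20:

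- HNSCC, true ORR 5%: P(X ≤ 2) = 0.925
- NSCLC, true ORR 10%: P(X ≤ 3) = 0.867
- MEL, true ORR 15%: P(X ≤ 4) = 0.830

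All three reproduce. They are defined for response-evaluable participants and, with the assumed ORRs read as rates in that set, the point made here does not alter them.

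**2. Who is left out.**

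| Treated participant with no on-study scan | Table 13 | Section 9.4.2 |
|---|---|---|
| Discontinued for progression | In | Non-responder if clinical deterioration is documented, otherwise not evaluable |
| Clinical deterioration documented, did not discontinue for progression | Out | Non-responder |
| Died without progression, withdrew consent or lost | Out | Not evaluable, unless clinical deterioration is documented |

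Participants who stop treatment for toxicity mostly stay in, because Section 8.1.1 schedules later scans, including one at safety follow-up.

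**3. Direction.** Let R be the responders, N all participants with at least one combination dose, and m those dropped. A response is a CR or PR confirmed at least 4 weeks later (Section 9.4.2), so the m participants contribute no responders. The reported rate is R/(N − m) and the all-treated rate is R/N. Hence R/(N − m) ≥ R/N, with equality when m = 0 or R = 0. When R > 0 the ratio is 1/(1 − d), where d = m/N. The same holds for DCR, because stable disease needs a measurement at 6 weeks or later.

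**4. Size.** The documents give no value of d, so m is assumed. The CI method is not named either; Clopper–Pearson 90% limits are used. The Part III rows take the planned 20 evaluable participants. The Part II rows assume one dose cohort at the stated "aim for at least 30 response-evaluable participants" with the confirmed phenotype, since participants whose fresh biopsy differs "will be assessed in a separate efficacy analysis population". The responder counts (4 and 6) are also assumed.

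| Illustration | m | d | Factor | ORR (90% CI) |
|---|---|---|---|---|
| Part III | 0 | 0% | 1.000 | 4/20 = 20.0% (7.1–40.1%) |
| Part III | 1 | 4.8% | 1.050 | 4/21 = 19.0% (6.8–38.4%) |
| Part III | 2 | 9.1% | 1.100 | 4/22 = 18.2% (6.5–36.9%) |
| Part II | 0 | 0% | 1.000 | 6/30 = 20.0% (9.1–35.7%) |
| Part II | 1 | 3.2% | 1.033 | 6/31 = 19.4% (8.8–34.7%) |
| Part II | 2 | 6.2% | 1.067 | 6/32 = 18.8% (8.5–33.7%) |
| Part II | 3 | 9.1% | 1.100 | 6/33 = 18.2% (8.2–32.8%) |

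For DCR, 10/20 = 50.0% becomes 10/21 = 47.6% or 10/22 = 45.5%.

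The ORR shifts run from 0.6 points (20.0 − 19.4) to 1.8 points (20.0 − 18.2). The intervals among evaluable participants are 33.0 points wide (40.1 − 7.1) and 26.6 points wide (35.7 − 9.1).

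**The case against.** The Section 9.4.2 rules have some use inside Table 13's set. They can code participants who left for progression without a scan, and those scanned whose response is missing or unknown, so they do not by themselves prove that a wider set was meant. That stands in part. But the example reasons in Table 14, such as withdrawal of consent, describe people Table 13 can exclude, and the denominator question stays open even for participants who were scanned.

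If not-evaluable participants were all kept in the denominator, there would be no upward shift. That is also true, and it is why the claim is that the ORR equals or exceeds the all-treated rate. That statement holds under either reading.

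The direction depends on all-treated meaning at least one dose of the combination. The safety set needs only one dose of study treatment, and Table 6 withholds RO7296682 after an incomplete atezolizumab dose. A responder given atezolizumab alone would therefore count in the safety set only (for example 2/20 = 10.0% against 3/21 = 14.3%). This is remote and arises from a different exclusion, but the new set must be defined by the combination dose.

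Finally, the study is exploratory, the shift is small and assumed, and no decision rule changes. Disposition on the safety set and the summary of non-evaluability reasons would show the gap. All of this limits the weight of the point. It does not supply the all-treated estimate and its CI, or settle which denominator is primary. For PFS and OS no size has been shown. Living participants without a scan would be censored one day after treatment start and add almost nothing to PFS; the early deaths are what matter.

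**Conclusion.** The concern holds. Followed as written, the plan removes only non-responders from the primary ORR, and likewise only participants without disease control from DCR. It also excludes early deaths without recorded progression from PFS and OS. The direction is certain when the comparison set is everyone given at least one combination dose. The size is unknown because the documents give no rate of missing scans: the inflation factor is 1/(1 − d), at most 1.10 in the cases shown, and 1 if nobody is dropped. The shift is small beside the sampling error, but more participants in a cohort would not remove it. The mismatch between Table 13 and Section 9.4.2 is a separate defect that needs settling whatever d proves to be. This should be fixed, though it does not threaten the design.

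**What to change.** - In Table 13 and Section 9.4.2, pre-specify ORR and DCR in all participants who received at least one dose of the combination. Count those with no on-study assessment as non-responders and as not having disease control. Report this beside the response-evaluable result, within the dose and phenotype groups already planned.
- Analyse PFS and OS in all participants given at least one combination dose.
- Keep the response-evaluable set as the labelled denominator for opening Part III cohorts and for futility, with the cut-offs and the 92%, 87% and 83% unchanged.
- Align the Section 9.4.2 rules on clinical deterioration, not-evaluable status and absence of post-baseline assessments with Table 13, and state for each rate whether not-evaluable participants count in the denominator.

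The cost is wording in two places and one extra set of outputs, with no new data. Two ORRs will be reported and must be clearly labelled, and the all-treated one may look slightly less favourable.

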9.4 STATISTICAL ANALYSES

The data will be analyzed by the Sponsor and/or designated contract research organization. Any data analysis carried out independently by the Investigator should be submitted to the Sponsor before publication or presentation. The data will be summarized with respect to demographic and baseline characteristics, efficacy observations and measurements, safety observations and measurements, and PK and biomarker measurements. The baseline value of any variable will be defined as the last available value prior to the first administration of study drug.

9.4.1 Demographics and Baseline Characteristics

Demography and baseline characteristics (including age, sex, participant disposition, previous therapies, and medical history) will be analyzed using descriptive statistics. The

analysis will be based on the safety analysis population. Data will be summarized by dose cohort within each part.

This is a non-randomized dose escalation and dose expansion study; therefore, comparability of treatment groups does not apply.

9.4.2 Efficacy Analyses

The primary and secondary efficacy analyses listed in [Table 14](#) will include all participants in the efficacy population with participants grouped according to dose cohort (and schedule if applicable) within each study part.

Table 14 Efficacy Statistical Analysis Methods

Endpoint	Statistical Analysis Methods
According to RECIST Version 1.1 criteria (Appendix 13) and iRECIST (Appendix 14) 
• Objective response rate (ORR)• Disease control rate (DCR)• Duration of response (DoR)• On treatment progression free survival (PFS)	No formal statistical model and no formal hypothesis testing are planned in this study. Tumor response data will be reported using descriptive statistics. Response data will be listed. Participants with missing or no response assessments will be classified as not evaluable unless there is documented clinical deterioration, in which case participant will be classified as non-responders. Reasons for the non-evaluability will be summarized (e.g., withdrawal of consent, study discontinuation because of AE or physician decision). ORR and DCR will be summarized by using relative frequencies and 90% confidence interval (CI). Duration of response and PFS (on-treatment) will be summarized by using time-to-event analyses and Kaplan-Meier curves.
• Overall Survival (OS) (if available)	OS data may be tabulated and summarized using time-to-event analyses and Kaplan-Meier curves if data are collected and mature. Summaries will be carried out by cohort (and schedule if applicable) separately for each part.

Objective response rate (ORR) is determined as the rate of participants with an overall response of CR or PR. DCR is determined as the rate of participants with an overall response of either CR, PR, or SD rate. ORR and DCR will be derived for RECIST v1.1 and will be based on Investigators' assessment. Objective response (OR) is defined as a CR or PR as determined by the Investigator. For this protocol, confirmation of response is required at least 4 weeks after a first response occurred. To classify a response as SD, measurements will have to be classified as stable (according to RECIST v1.1) at least once after study entry at a minimum of 6 weeks after study entry. Participants with missing or no response assessments will be classified as not evaluable unless there is documented clinical deterioration, in which case participants will be classified as non-responders.

DoR will be calculated for participants who have a best overall response of CR or PR and defined as the time from first occurrence of a documented OR until the time of

documented disease progression or death (death within 30 days from last study treatment) from any cause, whichever occurs first. Censoring methods will be the same as the one applied for progression-free survival (PFS; on-treatment).

PFS on treatment will be defined as the time from study treatment initiation (C1D1) to the first occurrence of documented disease progression (based on RECIST v1.1 Investigator's assessment) or death from any cause, whichever occurs first. For participants who do not have documented progressive disease or death (within 30 days from last study treatment) during the study, PFS will be censored at the day of the last tumor assessment. Participants without any post baseline assessments or with all post-baseline assessments having unknown result/response but known to be alive at the clinical cut off for the analysis will be censored at the date of study treatment initiation plus one day.

Sensitivity analyses of response endpoints (ORR, DCR, DoR, and PFS) may include the evaluation of response according to iRECIST and the evaluation of response from an independent centralized review.

OS is defined as the time from the first dose of study treatment to the time of death from any cause. Participants who are still alive at the time of analysis will be censored at the time of their last study assessment (for active participants) or at the last date known alive (for participants in follow-up).

